# 2.2.1. Nonclinical Pharmacology

A summary of the nonclinical investigational programs can be found in the current IB.

# 2.2.2. Nonclinical Pharmacokinetics and Metabolism

Etrasimod is eliminated primarily hepatically by extensive metabolism involving oxidation of etrasimod, along with dehydrogenation and conjugation, and showed no human specific metabolite(s) compared to those observed in the toxicology species. The main CYP enzymes involved in the oxidative metabolism of etrasimod are CYP2C8 (38%), CYP2C9 (37%), and CYP3A4 (22%), and with CYP2C19 and CYP2J2 being minor contributors (1% each). There are no major circulating metabolites and etrasimod is the primary circulating drug entity.

Additional information of the nonclinical PK and metabolism of etrasimod is available in the current IB.

# 2.2.3. Nonclinical Safety

Etrasimod was well tolerated across the general toxicity program conducted in CD-1 mice, Sprague Dawley rats, and beagle dogs, with no etrasimod-induced mortality following repeat administration up to 91-days, 6-months, and 9-months at 20, 150, and 15 mg/kg/day in mice, rats, and dogs, respectively. Most etrasimod-related findings were considered nonadverse,

reversible upon cessation of treatment, and/or readily monitorable in the clinic. One of the most common adverse effects across species was decreased body weight and/or body weight gain, with associated decreases in food consumption. The primary target organs identified across all species were lymphoid tissues, lung, and liver. In addition, the heart was identified as a target organ in the dog. When administered at doses within and above the therapeutic range (up to  $858 \times$  in rats and  $380 \times$  in dogs over the total Cmax exposure at the proposed human dose for the treatment of UC) in safety pharmacology studies, etrasimod showed no effect on CNS, respiratory, or cardiovascular function.

The potential effects of etrasimod on the cardiovascular system were investigated in a series of in vitro and in vivo studies. In vitro, etrasimod increased hERG currents by 31.4% at 1 mm and 58.9% at 3 mm. These concentrations are approximately 193 × and 578 × over the free  $C_{max}$  exposure at the proposed human dose for the treatment of UC. An IC50 for hERG current inhibition could not be established for etrasimod since only increases in hERG channel current, rather than inhibition, were observed. Based on the G protein receptor signaling associated with the primary PD activity, etrasimod was observed to activate GIRK currents in vitro. GIRK1 and GIRK4 are the 2 homologous subunits of IKACh that interact with G $\beta\gamma$  to mediate the activation of the potassium channel. G-protein signaling via GIRK IKACh channel activation in cardiac cells is considered to be responsible for the transient cardiovascular effects seen with first dose of S1P receptor modulators., ,  At IKACh in primary human atrial cardiomyocytes, etrasimod exhibited an EC50 of 29.9 nM and there was no difference between S1P and etrasimod in the time course of IKACh activation. The maximal current induced by etrasimod, however, was 90% of that observed with carbachol and was 10 × lower (based on EC50) than S1P itself.

Etrasimod was not mutagenic or clastogenic in in vitro genetic toxicity studies and is not considered genotoxic in rats or to pose a genotoxic risk to humans. There were no etrasimod-related effects on spermatogenesis or fertility in males at any dose level evaluated. In the embryo-fetal development studies in rats and rabbits, administration of etrasimod during the period of organogenesis resulted in increased post implantation loss and decreased mean litter numbers and proportions of viable fetuses in both species. The embryo lethality and fetal malformations noted with etrasimod in the rat and rabbit embryo-fetal development studies are consistent with similar findings observed with approved S1P modulators and are believed to be a result of the important role of S1P1 in embryogenesis, including vascular and neural development.

Further details of the nonclinical safety program are provided in the current IB.

# 2.2.4. Clinical Overview

Safety, tolerability and PK of etrasimod were evaluated in 15 Phase 1 studies in healthy adult participants. Efficacy and safety of etrasimod was evaluated in 3 completed Phase 2, 6 ongoing Phase 2, 3 completed Phase 3 and 2 ongoing Phase 3 studies across several disease indications. Clinical pharmacology data established the PK properties of etrasimod with or without food and in specified participant subpopulations (eg, participants with renal or hepatic impairment), and included comprehensive drug interaction studies to inform dosing recommendations.

A complete summary of the clinical data relevant to etrasimod and its study in human participants is provided in the current edition of the IB.

## 2.2.4.1. Pharmacokinetic Overview of Etrasimod

Etrasimod is absorbed with a median Tmax of 4 hours after administration as an etrasimod 2 mg IR tablet in the fasted state, and up to 6 hours in the fed state. Food did not affect etrasimod exposure measures (Cmax and AUC). Plasma Cmax and AUC values of etrasimod are dose proportional following a single dose of 0.1 to 5 mg. For multiple-doses of etrasimod over a range of 0.7 to 2 mg once daily, steady-state Cmax increased dose proportionally and steady-state AUC0-24 increased slightly greater than dose proportionally. Apparent dose proportional increases were also observed for mean steady-state Cmax and AUC0-24 values from 2 to 4 mg once daily dosing in healthy participants. The time to reach approximate steady-state for etrasimod exposure measures (Cmax, AUC0-24, Ctrough) is within 7 days of the first dose. Mean Rac for etrasimod exposure measures are <3-fold with once daily dosing. These observations are consistent with etrasimod's elimination (effective) half-life of approximately 30 hours. The mean oral Vz/F of etrasimod ranged from 50 to 103 L in healthy participants across evaluated single and multiple-dose levels and Phase 1 studies, indicating extravascular distribution. The mean oral plasma CL/F of etrasimod following single and multiple-dose administration of etrasimod was low and ranged from 1.13 to 1.43 L/h and 0.97 to 1.70 L/h, respectively, in healthy participants across evaluated dose levels in the Phase 1 studies.

The human mass balance study identified 2 oxidative metabolites, AR503641 (M3) and AR504344 (M6) present in systemic circulation, though minor as they are each <10% of total radioactivity. The oxidation of etrasimod occurs by 3 CYPs (CYP2C8, CYP2C9 and CYP3A4). Etrasimod is primarily eliminated in feces, with no parent drug detected in the urine.

# 2.2.4.2. Safety Overview of Etrasimod

As of 30 Aug 2022, a total of 2119 participants (419 healthy participants and 1700 participants with disease) have been exposed to etrasimod in clinical development programs. Clinical evidence in participants of healthy status, UC, CD, AD, AA or EoE to date have demonstrated that etrasimod is well tolerated in humans.

Across all clinical studies (Phase 1 to Phase 3), etrasimod caused expected mild, transient, and generally asymptomatic reduction in HR at first dose and very few participants with HR < 50 bpm. These reductions were greatest following first dose and lessened upon repeat dosing due to development of tolerance, allowing HR to return to baseline. The HR effects are related to S1P1 localized on atrial myocytes that activate GIRK channels, which are transient and not clinically adverse or associated with safety findings.

Etrasimod 2 mg administered once daily demonstrated an acceptable safety profile up to 52 weeks in controlled studies and up to 104 weeks in uncontrolled studies. There was a low incidence of SDEIs such as infections, including severe (ie, Grade  $\geq$ 3) infections, opportunistic infections, and herpes infections (herpes zoster and herpes simplex), cardiac

safety events (bradycardia, AV conduction delays, and hypertension), malignancies, liver injury (liver transaminase elevation and bilirubin elevation), macular oedema, and pulmonary disorders (airflow obstruction and decreased gas exchange) in participants who were treated with etrasimod 2 mg.

## 2.3. Benefit/Risk Assessment

Etrasimod, an investigational, oral, and once daily S1P receptor modulator, is not expected to provide any clinical benefit to healthy participants. In this study, etrasimod will be administered at single doses of 2 mg. This study is designed primarily to generate safety, tolerability, pharmacokinetic, and palatability data for the etrasimod mini tablets to support future pediatric studies.

Etrasimod was determined to be well tolerated and to have an acceptable safety profile in both healthy participant and diseased clinical studies.

More detailed information about the known and expected benefits and risks and reasonably expected AEs of etrasimod may be found in the IB, which is the SRSD for this study. Refer to the Study Intervention(s) table in Section 6.1 for a complete description of SRSDs.

# 2.3.1. Risk Assessment

Potential Risk of Clinical Significance	Mitigation Strategy									
Study Intervention(s) Etrasimod										

 
S1P receptor modulator-related effects (class effect of AEs observed with S1P receptor modulators) may be observed.
 
cardiovascular events (eg, bradycardia, atrioventricular conduction delay and hypertension)
 
infections (severe infections, opportunistic infections, Herpes simples and Herpes zoster)
 
macular edema
 
pulmonary events (airflow obstruction or altered gas exchange)
 
liver injury
 
malignancy
 
	
 
Clinical experience with other S1P receptor modulators for the treatment of MS and UC.
 
The totality of etrasimod clinical studies (Phase 1, 2 and 3 studies) have shown that 2 mg etrasimod is well-tolerated with no clinically significant safety signals.
 
	Exclusion of participants at risk. Short duration of treatment. Safety labs at screening and baseline and when deemed necessary by the investigator throughout the study. AE monitoring throughout the study.								
S1P receptor modulator-specific lymphocyte level decreases.	Dose-dependent reductions in peripheral lymphocyte counts are an expected PD effect of etrasimod. The totality of clinical studies following single dose administration of study intervention is well-tolerated with a return to normal range by Day 7.	Participants with conditions or risk factors related to infection or immune function will be excluded from the study. Participants will be assessed for safety including infections at regular intervals throughout the study to identify and mitigate the potential risks.								
First dose cardiac effect	S1P receptor modulators class of drugs is associated with an expected, on-target effect of reducing HR when first dosed. The totality of clinical data up to date across Phase 1 to 3 studies across several indications indicate that etrasimod 2 mg is well-tolerated with modest HR reduction that is maximal on the first day of	Participants with elevated cardiac risk factors will be excluded from participation in the study. Hourly HR monitoring for the first 6-hours post first dose will be conducted for all dose periods. Participants with cardiac effects associated with first dose will be required to permanently discontinue study intervention.								

Potential Risk of Clinical Significance	Summary of Data/Rationale for Risk	Mitigation Strategy
	dosing without major clinically relevant cardiac safety events.	
Reproductive and developmental toxicity.	The effects of etrasimod on human fertility and embryonic development are unknown.	WOCBP who are pregnant, lactating, or breastfeeding will be excluded from this study.
	Nonclinical reproductive and developmental toxicity studies of etrasimod combined with data and knowledge on the role of S1P 1 in vascular embryogenesis demonstrate embryo fetal toxicity of etrasimod if used during pregnancy. Etrasimod is potentially teratogenic in humans with a low genotoxic potential. There is no margin of safety for these findings compared to therapeutic exposure range. Etrasimod should not be given to women who are pregnant, lactating or breastfeeding	

WOCBP will be eligible only if she and her partner(s) agree(s) with the contraceptive method as described in Section 10.4.4 throughout the study period and for at least 28 days after the last dose of etrasimod.

Males with female partners of childbearing potential must agree to use contraception throughout the study period and for at least 28 days after the last 28 days after the last dose of etrasimod.

	Study Procedures Blood Collection for PK	
Extravasation, bruising, local discomfort	Collection of 14 PK plasma samples per period per sequence	Use of highly qualified nurses, with venipuncture experience.
	Collection of 8 PK micro samples collected for Treatment A.	Use of alternating arms for adjacent time points can provide more resting and healing time for each arm between samplings.

### 2.3.2. Benefit Assessment

Etrasimod is not expected to provide any clinical benefit to healthy participants. This study is designed primarily to generate safety, tolerability, and PK data for further clinical development of etrasimod mini tablets. In this study, etrasimod will be administered at single doses of 2 mg.

# 2.3.3. Overall Benefit/Risk Conclusion

Taking into account the measures to minimize risk to study participants, the potential risks identified in association with etrasimod are justified by the anticipated benefits that may be afforded to participants with UC.

# **3. OBJECTIVES AND ENDPOINTS**

Objectives	Endpoints
Primary:	Primary:

 
To estimate the rBA of etrasimod 2 mg mini tablets mixed with water compared to etrasimod 2 mg clinical IR tablets under fasted conditions
 
To estimate the rBA of the etrasimod 2 mg mini tablets mixed with applesauce compared to the etrasimod 2 mg clinical IR tablets under fasted conditions
 
To estimate the rBA of the etrasimod 2 mg mini tablets mixed with chocolate pudding compared to the etrasimod 2 mg clinical IR tablets under fasted conditions
 
To estimate the rBA of the etrasimod 2 mg mini tablets mixed with chocolate pudding compared to the etrasimod 2 mg clinical IR tablets under fasted conditions
 
To estimate the rBA of the etrasimod 2 mg mini tablets mixed with yogurt compared to the etrasimod 2 mg clinical IR tablets under fasted conditions
 
	• Plasma AUC last , AUC inf and C max of etrasimod
Secondary:	Secondary:
• To evaluate the safety and tolerability of etrasimod in healthy participants	• Assessment of first dose HR reduction, TEAEs, clinical laboratory abnormalities, vital signs, PEs, and 12-lead ECGs
• To assess the palatability of etrasimod mini tablets mixed with water/applesauce/chocolate pudding/yogurt	• Assessment of palatability via questionnaire: mouth feel, bitterness, tongue/mouth burns, throat burn, and overall liking
Tertiary/Exploratory:	Tertiary/Exploratory:
• To characterize the PK parameters of etrasimod 2 mg mini tablets mixed with water or soft foods (applesauce, chocolate pudding, or yogurt) compared to etrasimod 2 mg clinical IR tablet	
 
Plasma etrasimod: t1/2, CL/F, Vz/F and Tmax of etrasimod
 

• To validate the PK measurement of etrasimod in capillary blood sample collected using micro sampling device against the PK measurement of etrasimod in venous blood samples.	• Plasma concentration of etrasimod obtained via micro sampling compared to venous sampling

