### 4. STUDY DESIGN

### 4.1. Overall Design

This is a Phase 1, open-label, single-dose, randomized 4-crossover periods and 1-fixed period design in a single cohort of approximately 16 healthy male or female participants .

The study will consist of 5 treatments as shown below:

- 1. Treatment A: Single oral dose of etrasimod 2 mg clinical IR tablet under fasted conditions (Reference)
- 2. Treatment B: Single oral dose of etrasimod 2 mg mini tablets mixed with applesauce under fasted conditions (Test 1)
- 3. Treatment C: Single oral dose of etrasimod 2 mg mini tablets mixed with chocolate pudding under fasted conditions (Test 2)
- 4. Treatment D: Single oral dose of etrasimod 2 mg mini tablets mixed with water under fasted conditions (Test 3)
- 5. Treatment E: Single oral dose of etrasimod 2 mg mini tablets mixed with yogurt under fasted conditions (Test 4)

Sixteen participants will be enrolled in Period 1 for a total of 12 evaluable participants to complete study. Participants will be randomly assigned to 1 of the 4 sequences shown in Table 2 in which participants are randomized in crossover design to receive Treatments A to D in Periods 1 to 4 with Treatment E being fixed in Period 5. Participants will be discharged on Day 9 of Period 5, following completion of all assessments. Each treatment is 9 days that includes dosing, PK sampling and an extra day to minimize any residual etrasimod concentrations prior to start of the next treatment. The total planned duration of participation from the screening visit to the last follow-up phone call, is approximately 14 weeks.

Treatment sequence (n=4 per sequence)	Period 1	Period 2	Period 3	Period 4	Period 5 (fixed)
1	А	В	С	D	Е
2	В	D	А	С	Е
3	С	А	D	В	Е
4	D	С	В	А	Е

 Table 2.
 Treatment Sequence

Since etrasimod has a half-life approximately 30 hours, there will be a 9-day washout between each dose.

Blood samples for PK analysis will be collected predose and at 1, 2, 4, 6, 8, 12, 24, 48, 72, 96, 120, 144 and 168 hours postdose (SoA). Capillary blood samples (using micro sampling Tasso device) will be collected at predose and at 1, 2, 4, 6, 8, 12 and 24 hours postdose (SoA) for PK assessments (Treatment A). Micro PK sampling occurs after PK blood sampling, and taken from the other arm.

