# 9.3.3. Pharmacokinetic Analyses

Plasma PK parameters of etrasimod will be derived (as data permit) from the concentration-time data using standard noncompartmental methods as outlined in the Table 3 below. Actual PK sampling times will be used in the derivation of PK parameters. In the case that actual PK sampling times are not available, nominal PK sampling time will be used in the derivation of PK parameters.

Parameter	Definition	Method of Determination
AUC inf	Area under the concentration-time curve from time zero extrapolated to infinity	AUC last + ( $C_{last}$ */ $k_{el}$ ), where $C_{last}$ * is the predicted plasma concentration at the last quantifiable time point from the log-linear regression analysis
AUC last	Area under the plasma concentration-time profile from time zero to the time of the last quantifiable concentration (C last )	Linear/Log trapezoidal method.
C max	Maximum observed concentration	Observed directly from data
T max	Time for C max	Observed directly from data as time of first occurrence
t 1/2	Terminal half-life	$Log_e(2)/k_{el}$ , where $k_{el}$ is the terminal phase rate constant calculated by a linear regression of the loglinear

 Table 3.
 Plasma Etrasimod PK Parameters Definitions

Parameter	Definition         Method of Determination	
		concentration-time curve. Only those data points judged to describe the terminal loglinear decline will be used in the regression.
CL/F	Apparent clearance	Dose/AUC inf
V z /F	Apparent volume of distribution	$Dose/(AUC_{inf} \bullet k_{el})$

 Table 3.
 Plasma Etrasimod PK Parameters Definitions

PK parameters will be summarized descriptively by treatment, in accordance with Pfizer data standards. Plasma concentrations will be listed and summarized descriptively by nominal PK sampling time and treatment. Individual participant and median profiles of the plasma concentration-time data will be plotted by treatment using actual and nominal times, respectively. Median profiles will be presented on both linear-linear and log-linear scales.

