Natural log transformed AUCinf, AUClast and Cmax will be analyzed using a mixed effect model with sequence, period and treatment as fixed effects and participant within the sequence as a random effect. Estimates of the adjusted mean differences (Test-Reference) and corresponding 90% CIs will be obtained from the model. The adjusted mean differences and 90% CIs for the differences will be exponentiated to provide estimates of the ratio of adjusted geometric means (Test/Reference) and 90% CI for the ratios. Treatment A (etrasimod 2 mg clinical IR tablets under fasted conditions) will be the Reference treatment while Treatment B (etrasimod 2 mg mini tablets mixed with applesauce under fasted conditions), Treatment C (etrasimod 2 mg mini tablets mixed with chocolate pudding under fasted conditions), and Treatment D (etrasimod 2 mg mini tablets mixed with water under fasted conditions) will be the Test treatments.

Natural log transformed AUCinf, AUClast and Cmax will be analyzed using a mixed effect model with sequence and treatment as fixed effects and participant within the sequence as a random effect. Treatment A (etrasimod 2 mg clinical IR tablets under fasted conditions) will be the Reference treatment while Treatment E (etrasimod 2 mg mini tablets mixed with yogurt under fasted conditions) will be the Test treatment.

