6. ANALYSES AND SUMMARIES

6.1. Primary Endpoints

Plasma AUC_{last}, AUC_{inf} and C_{max} of etrasimod will be summarized by treatment group and will include the set of summary statistics as specified in Table 4.

For the evaluation of relative bioavailability of etrasimod 2 mg mini tablets mixed with applesauce, chocolate pudding and water compared to etrasimod 2 mg clinical IR tablets, *natural log transformed AUC_{inf}, AUC_{last} and C_{max} will be analyzed using a mixed effect model with sequence, period and treatment as fixed effects and participant within the sequence as a random effect. Estimates of the adjusted mean differences (Test Reference) and corresponding 90% CIs will be obtained from the model. The adjusted mean differences and 90% CIs for the differences will be exponentiated to provide estimates of the ratio of adjusted geometric means (Test/Reference) and 90% CI for the ratios. Treatment A (etrasimod 2 mg clinical IR tablets under fasted conditions) will be the Reference treatment while Treatment B (etrasimod 2 mg mini tablets mixed with applesauce under fasted conditions), and Treatment D (etrasimod 2 mg mini tablets mixed with water under fasted conditions) will be the Test treatments.*

For the evaluation of relative bioavailability of etrasimod 2 mg mini tablets mixed with yogurt compared to etrasimod 2 mg clinical IR tablets, *natural log transformed AUC*_{inf}, AUC_{last} and C_{max} will be analyzed using a mixed effect model with sequence and treatment as fixed effects and participant within the sequence as a random effect. Treatment A (etrasimod

DMB02-GSOP-RF02 7.0 Statistical Analysis Plan Template 31-Jan-2022 PFIZER CONFIDENTIAL TMF Doc ID: 98.03 Page 12 of 20 2 mg clinical IR tablets under fasted conditions) will be the Reference treatment while Treatment E (etrasimod 2 mg mini tablets mixed with yogurt under fasted conditions) will be the Test treatment.

For AUC_{inf}, AUC_{last} and C_{max} , a listing of the individual participant ratios (Test/Reference) will be provided. Box and whisker plots for AUC_{inf}, AUC_{last} and C_{max}, will be plotted by treatment and overlaid with geometric means.

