6.3. Other Endpoints

6.3.1. Other PK parameters of etrasimod

Exploratory endpoints include other PK parameters of etrasimod such as T_{max} , $t_{1/2}$, CL/F and V_z /F. The PK parameters will be listed and summarized descriptively by treatment group in accordance with Pfizer data standards on the PK Parameter Set, as data permit. Missing values will be handled as detailed in Section 5.3.1. Each PK parameter will be summarized by treatment group and will include the set of summary statistics as specified in Table 4.

Parameter	Summary Statistics
AUC _{inf} , AUC _{last} , C _{max} ,	N, arithmetic mean, median, SD, %CV, minimum, maximum,
CL/F, V _z /F T _{max}	geometric mean and geometric %CV N, median, minimum, maximum
t _{1/2}	N, arithmetic mean, median, SD, %CV, minimum, maximum

 Table 4.
 PK Parameters to be Summarized Descriptively by Treatment

Supporting data from the estimation of $t_{/_2}$ and AUC_{inf} will be listed by analyte and group: terminal phase rate constant (k_{el}); goodness of fit statistic from the log-linear regression (r²); the percent of AUC_{inf} based on extrapolation (AUC_{extrap}%); and the first, last, and number of time points used in the estimation of k_{el}. This data may be included in the clinical study report.

PK Concentrations:

The plasma concentrations will be listed and descriptively summarized by nominal PK sampling time and treatment. Individual participant, as well as mean and median profiles of the plasma concentration-time data will be plotted by treatment using actual (for individual) and nominal (for mean and median) times respectively. Mean and median profiles will be presented on both linear and semi-log scales.

Presentations of concentrations will include:

- A listing of all concentrations sorted by participant ID, treatment and nominal time postdose. The concentration listing will also include the actual times. Deviations from the nominal time will be given in a separate listing.
- A summary of concentrations by treatment and nominal time postdose, where the set of statistics will include n, mean, median, SD, %CV, minimum, maximum and the number of concentrations above the LLQ.
- Median concentrations time plots (on both linear and semi-log scales) against nominal time postdose by treatment (all treatments on the same plot per scale, based on the summary of concentrations by treatment and time postdose).

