- Mean concentrations time plots (on both linear and semi-log scales) against nominal time postdose by treatment (all treatments on the same plot per scale, based on the summary of concentrations by treatment and time postdose).
- Individual concentration-time plots by treatment (on both linear and semi-log scales) against actual time postdose (there will be separate spaghetti plots for each treatment per scale).
- Individual concentration-time plots by participant (on both linear and semi-log scales) against actual time postdose [there will be separate plots for each participant (containing all treatments) per scale].

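### Tmax is to be compared with the IR tablet, but no within-participant difference or interval is summarized, so a shift smaller than the 2 h sampling step can go unseen

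*Protocol*

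**What the plan says.** Protocol Section 3 states the exploratory objective as "To characterize the PK parameters of etrasimod 2 mg mini tablets mixed with water or soft foods (applesauce, chocolate pudding, or yogurt) compared to" the 2 mg IR tablet, with endpoints t1/2, CL/F, Vz/F and Tmax. SAP 2.2 repeats it.

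The analysis is descriptive. Protocol 9.3.3 says "PK parameters will be summarized descriptively by treatment, in accordance with Pfizer data standards". SAP 6.3.1 says "The PK parameters will be listed and summarized descriptively by treatment group in accordance with Pfizer data standards", and its Table 4 gives Tmax the statistics "N, median, minimum, maximum".

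Paired results are planned for AUCinf, AUClast and Cmax only. For these, "Estimates of the adjusted mean differences (Test-Reference) and corresponding 90% CIs will be obtained from the model" (Protocol 9.3.3), and "a listing of the individual participant ratios (Test/Reference) will be provided" (SAP 6.1).

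The pairing is not lost for the other parameters. SAP 6.3.1 lists them by participant and plans concentration-time plots in which "there will be separate plots for each participant (containing all treatments) per scale".

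On sampling, Protocol 4.1 says "Blood samples for PK analysis will be collected predose and at 1, 2, 4, 6, 8, 12, 24" hours and later. Protocol 2.2.4.1 gives a median Tmax of 4 h for the fasted IR tablet.

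**The concern.** The objective asks for a comparison and the design makes each participant their own control, yet the planned Tmax output is a set of separate medians and ranges. Around 4 h the observed Tmax can take only a few values (2, 4, 6, 8 h), so a median tends to stay on one value or jump by a full or half step. The report could show the same Tmax summary for two treatments when nearly all the changes go the same way. It could also show a 1-2 h difference that is only grid noise, with no interval to tell the two apart. Tmax is the listed endpoint that most directly describes absorption timing, and the study supports a new pediatric formulation.

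**Working it through.** The plan states no precision for Tmax; Protocol Table 4 covers AUC and Cmax only. The check therefore sets out what is planned, then uses a counted example and a simulation.

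**1. What is planned against Treatment A**

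| Parameter | By-treatment summary | Individual ratio listing | Model contrast with 90% CI |
|---|---|---|---|
| AUCinf, AUClast, Cmax | yes | yes | yes |
| CL/F | yes | no | follows from AUCinf |
| Tmax, t1/2, Vz/F | yes | no | no |

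CL/F is Dose/AUCinf, and the dose is 2 mg in every period. Its Test/Reference ratio is therefore exactly 1/(AUCinf ratio): an AUCinf ratio of 0.90 gives 1/0.90 = 1.11, and the interval limits invert in the same way.

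**2. Counted example (no variance assumption)**

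Take 16 participants with these Tmax pairs, A to Test: one 2→2, two 2→4, seven 4→4, four 4→6, two 6→6.

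- A has 3 at 2 h, 11 at 4 h and 2 at 6 h: N 16, median 4, range 2-6.
- Test has 1 at 2 h, 9 at 4 h and 6 at 6 h: N 16, median 4, range 2-6.
- The Table 4 output is identical, yet six participants peak later and none earlier. Exact two-sided sign test: 2 × (1/2)^6 = 0.031.
- The differences are ten zeros and six of +2 h, so their plain median is also 0. The 16 × 17/2 = 136 pairwise averages are 55 zeros, 60 ones and 21 twos. Their median, the Hodges-Lehmann estimate, is 1 h.
- The signed-rank critical value for n = 16 at two-sided 10% is 35, so the 90% CI runs from the 36th smallest to the 36th largest average: 0 to 1 h. It touches zero, which shows how coarse such an interval is. The counts (3/11/2 against 1/9/6) show the shift more plainly.

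**3. Simulation (illustrative)**

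From the documents: the sampling grid, median Tmax 4 h, half-life 30 h, and 12 evaluable of 16 enrolled. Assumed: one-compartment profiles, lognormal Tmax with between- and within-participant SD 0.25 on the log scale, and multiplicative concentration error of 3% or 6%. Observed Tmax is the nominal time of the highest value. There were 4,000 crossovers per scenario. A Tmax ratio of 0.75 is a shift of about -1 h, and a ratio of 0.5 about -2 h.

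| True shift | Error | Medians equal, n=12 / n=16 | Hodges-Lehmann estimate zero, n=12 / n=16 |
|---|---|---|---|
| about -1 h | 3% | 51% / 59% | 20% / 16% |
| about -1 h | 6% | 37% / 43% | 25% / 21% |
| about -2 h | 3% | 2% / 1% | 0% / 0% |
| about -2 h | 6% | 7% / 6% | 2% / 0% |
| none | 3% | 56% / 61% | 59% / 65% |
| none | 6% | 40% / 42% | 49% / 55% |

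A second model rounds Tmax to the nearest sample, with log-SD 0.3-0.4 between and 0.2-0.3 within participants. For a 1 h delay the medians are equal in 37-41% of trials, while a signed-rank analysis at two-sided 10% flags the shift in 49-72% (n = 12) or 58-84% (n = 16). For a 0.5 h delay it flags only 22-39%. For a 2 h delay the medians are equal in 1-3%.

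**4. Would Cmax show it instead?**

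In a one-compartment model Cmax is proportional to exp(-kel × Tmax), with kel = ln 2/30 = 0.0231 per h. A shift of -1.1 h changes Cmax by exp(0.0231 × 1.1) - 1 = 2.6%. Protocol Table 4 gives a Cmax interval of 93.14% to 107.36% at a ratio of 100%, so Cmax would not reveal such a shift. The shift would also matter little for peak exposure.

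**The case against.** A reader might infer that the plan discards the crossover pairing. It does not: every participant's parameters are listed, and each participant's profiles under all treatments are plotted together on two scales. What is missing is a summary of the pairing. A reader might also extend the point to all the exploratory parameters. CL/F is already covered through AUCinf, and no harm has been shown for t1/2 or Vz/F.

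The tier counts too. The primary objectives are to estimate and get models with intervals; this one is to characterize, and no hypothesis is tested. Side-by-side description is a defensible way to meet an exploratory objective. No documented decision turns on Tmax: Protocol 4.3 says the pediatric doses are chosen to match adult AUC, and Protocol 2.2.4.1 reports a later Tmax with food but no effect on Cmax or AUC. This limits the severity. It does not make two separate medians a good comparison, and an interval is not a test.

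The percentages depend on the model. With no true shift the medians still differ in 39-44% of trials at 3% error, but the Hodges-Lehmann estimate is also non-zero in 35-41%. The paired point estimate carries grid noise too, so what is gained there is the interval. Tmax will also be derived from actual sampling times. Protocol 8.5 tolerates 10% up to 10 h, which is 24 minutes at 4 h, so in practice equal medians means equal to within minutes. All of this stands.

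**Conclusion.** The point holds for Tmax, at low severity. The objective is comparative, but the plan summarizes no within-participant Tmax difference and gives no interval against Treatment A. The counted example shows, without any variance assumption, that the planned output can be identical for two treatments when every change goes one way. As an illustration of size, a shift of about -1 h leaves the medians equal in roughly 40-60% of trials, against a zero paired estimate in roughly 16-25%. These figures rest on assumed Tmax variability and assay error, neither of which the documents give. The weakness is confined to shifts smaller than the sampling step. The documents do not support saying that the pairing is thrown away, that a large shift would be missed, or that the primary bioavailability results are affected.

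**What to change.** Add to SAP 6.3.1, labelled exploratory:

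- For B, C and D against A, list the within-participant Tmax difference and report the Hodges-Lehmann median difference with a nonparametric 90% CI. The plain median of the differences is not enough, as the counted example shows.
- Give a count of participants by nominal Tmax (1, 2, 4, 6, 8, 12 h) for each treatment.
- Report E against A in the same way, stating that E is always in Period 5 and so confounded with period.

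CL/F needs no addition, and within-participant t1/2 ratios are optional.

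The cost is one paragraph and one table, from data already collected. The downside is a few extra exploratory intervals that will be coarse, with heavy ties and 12-16 participants. The grid also limits what the paired analysis can detect at shifts near 0.5 h, and the text should say so.
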